6.5 Strategies to improve adherence

1. The PI will educate the subject on the importance of correctly administering concomitant treatment to achieve the study objectives.
2. Direct questioning by the PI regarding the application of concomitant treatment.
3. Delivery of a printed calendar specifying the date of the visit and its activities.

If deemed necessary, text messages may be sent as reminders. The content of these messages must be approved in advance by the IEC.

7. Methods and procedures of the study

7.1 Research center

This study will be conducted at one or more research centers previously evaluated by the sponsor. The center will be an institution or facility that conducts health research and complies with current regulations.

The research center will be responsible for forming a multidisciplinary research team to execute the clinical study according to the protocol. It is its prerogative to design the organization and select the personnel who will perform these functions. However, the sponsor requires that the PI and sub-investigator be physicians specializing in ophthalmology.

Any person assigned, under the PI's responsibility, to a part of the study monitoring (sub-investigator, nurse, etc.) or a specific role in the study (pharmacist, administrative assistant, study coordinator, etc.) must be listed in the "Delegation of Responsibilities."

The competency and training of all individuals directly involved in study activities must be verified prior to the conduct of any protocol-related activities. This must be recorded, and documents constituting evidence of this competency and/or training must be retained in the study master file. The competency and training of personnel involved in the study, both at the central level and at the study sites, is the responsibility of the sponsor.

The sponsor must ensure that all study site personnel participating in the study are adequately trained in the study (research protocol, investigator's manual, amendments, standard operating procedures, etc.) and in ICH Good Clinical Practices prior to the start of their participation in the study. Training must be documented in writing and filed in the study master file.

7.2 Clinical study registration

This clinical study will be registered by the sponsor in public clinical trial registries prior to its initiation (inclusion of the first subject): the National Registry of Clinical Trials (RNEC) of the Federal Commission for the Protection against Sanitary Risks (COFEPRIS) and on a WHO primary registry platform. WHO primary registries meet specific criteria regarding content, quality and validity, accessibility, unique identification, technical capacity, and administration. WHO primary registries meet the requirements of the International Committee of Medical Journal Editors (ICMJE).

7.3 Randomization and blinding

Treatment allocation/randomization will be performed centrally using an integrated web-based response system (IWRS). There are two treatment groups. Participants will be randomly assigned 1:1 to treatment with PRO-149 or Healon® EndoCoat, with equal probability of being assigned to either treatment.

After signing the ICF, the subject will receive a patient number under which all information will be coded pseudo-anonymously during collection and completely anonymized during analysis.

The generation will be carried out by a third party, authorized by Laboratorios Sophia, S.A. de C.V., through its electronic system, using a list of random numbers (SAS Institute Inc, Cary, NC, USA). Information corresponding to this third party will be found on file.

This is an open-label study, meaning there is no blinding, except for the statistical analysis. The investigational products will be identified by labels that comply with current and applicable regulations. These labels must contain, at a minimum, the following:

- Name, address and telephone number of the sponsor.

- Pharmaceutical form and route of administration.
- Number of doses.
- Batch number.
- Legend "Exclusively for clinical studies"
- Expiration date.

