5.1 Eligibility criteria

5.1.1 Inclusion criteria

- Age equal to or greater than 49 years.
- Diagnosis of age-related cataract (senile cataract) requiring cataract phacoemulsification surgery and placement of a monofocal intraocular lens.
Grade I to IV cataracts based on nuclear opacity (opalescence and/or color) of the lens opacity classification system (LOCS III).
- Ability to voluntarily grant informed consent.
- Be able and willing to comply with scheduled visits, treatment plan, and other study procedures.
- Desire and willingness to undergo phacoemulsification surgery and placement of a monofocal IOL.
- Have an anterior chamber depth \geq 2.8 mm as measured by IOL Master.
- Preoperative cardiology evaluation that qualifies the patient for the surgical procedure, with supporting laboratory studies: complete blood count (CBC), three-element blood chemistry (BC), coagulation times (PT/PTT, INR), and electrocardiogram (ECG). If a prior evaluation is available, it must not be performed more than 45 days prior to signing the informed consent form (ICF).

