10.1.2 Data interpretation

The results of continuous quantitative variables will be presented in measures of central tendency: mean, standard deviation and ranges.

KS and SW tests will be performed, as applicable, to determine whether the distribution presents normality in the results obtained in each study group. [44]

If normality of the data is observed ($p > 0.05$; for KS and SW), the statistical analysis of the continuous quantitative variables to find significant differences (p) will be as follows:

- Intra-group analysis: will be determined using the Student's t-test for repeated measures.
- Between-group analysis: differences between groups will be analyzed using Student's t-test for independent groups.

For $p < 0.05$ in KS and SW, the statistical analysis of continuous quantitative variables to find significant differences (p) will be as follows:

- Intra-group analysis: will be determined using the Wilcoxon rank test. [45]
- Between-group analysis: differences between groups will be analyzed using the Mann-Whitney U statistic.

The level of difference to consider significance will be an α of 0.05 or less [46].

The results of the nominal and ordinal qualitative variables will be presented in frequencies, proportions and percentages.

Statistical analysis to identify significant differences in qualitative variables will be performed by creating 2x2 contingency tables and will be carried out as follows:

- Intra-group differences: will be determined by the McNemar test [47], which is applied to 2x2 contingency tables with a dichotomous trait and pairs of matched subjects to determine whether the marginal frequencies of row and column are equal (marginal homogeneity).
- Difference between groups: Differences between groups will be analyzed using Pearson's X^2 test or Fisher's exact test when expected values are less than 5.

The level of difference to consider significance will be an α of 0.05 or less.

For the reporting of adverse events, participants who were randomly assigned to an intervention group after application of the investigational product will be considered.

The final results report will be displayed in tables or graphs, as appropriate.

The investigational product will be considered safe when there are no clinical and statistical differences in all primary outcome variables, with respect to its comparator (Healon EndoCoat®).

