10.1.5 Subjects included in the analysis

Those subjects who complete all their visits will be included in the statistical analysis to meet the study objective (PP; per-protocol population).

The variables, method and scales for their measurement are described in detail below.

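### Nuclear cataract grade has to be judged for eligibility but is not used in the between-arm comparison of CEC change; with about 18 eyes per arm, a pre-specified adjustment is worth considering

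*Combined protocol and SAP*

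**What the plan says.** Eligibility (5.1.1, and the synopsis in 1.1) covers "Grade I to IV cataracts based on nuclear opacity (opalescence and/or color) of the lens opacity classification system (LOCS III"). Section 2.1.2 notes that the LOCS III system has helped surgeons plan around the operation. It says nothing about endothelial loss by grade.

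Allocation (7.3) is central, through an IWRS: "Participants will be randomly assigned 1:1 to treatment with PRO-149 or Healon® EndoCoat, with equal probability of being assigned to either treatment". No stratum, block or minimisation factor is named. Randomisation takes place at the surgery visit (7.5.1.3), after eligibility is complete.

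CEC change is one of the two primary outcomes (7.4.1). For continuous variables, 10.1.2 gives two branches. With normal data: "Between-group analysis: differences between groups will be analyzed using Student's t-test for independent groups". Otherwise, "differences between groups will be analyzed using the Mann-Whitney U statistic". Neither branch carries a covariate, and Table 3 in 7.4.4 does not list cataract grade as a variable.

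The conclusion depends on this comparison: "The investigational product will be considered safe when there are no clinical and statistical differences in all primary outcome variables". The analysis set is the completers: "Those subjects who complete all their visits will be included in the statistical analysis to meet the study objective" (10.1.5). There are 18 eyes per arm (10.2.1), of which 14 are treated as the number required (10.1.4).

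**The concern.** The trial must assess a baseline characteristic of the lens in every eye, and it spans four grades. If harder nuclei go with more cell loss, arms of this size can easily differ in the share of hard eyes. The planned tests could not then separate that difference from a device effect.

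The error could go either way. An imbalance could create a CEC difference between equivalent products. It could also hide a real one, and because the product is called safe when no difference is found, hiding one leads to a favourable verdict. If grade is prognostic, leaving it out of the analysis also costs precision in a small trial.

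**Working it through.** **Inputs from the documents.** 36 eyes, 18 per arm (10.2.1); unadjusted tests at 0.05 (10.1.2); a 5% margin, which appears only in 10.2.2. The plan gives no figure for balance on grade. Its step from 14 to 18 eyes reproduces as 14/(1 - 0.20) = 17.5, rounded up to 18. How the 14 was obtained is a separate question.

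**Assumed inputs.** The share of hard eyes (grade III-IV), the extra CEC loss in hard eyes (0 to 10 percentage points), and the SD of CEC change (10 to 12.5 points overall; 6 to 10 points within grade for the simulations). None of these is in the documents.

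**1. Chance of imbalance, arms fixed at 18/18.** With K hard eyes among 36, the number in one arm is hypergeometric (36, K, 18). A gap of 4 eyes is 4/18 = 22 points.
- K = 18: a gap of at least 4 means 7 or fewer, or 11 or more, in one arm. P = 2 × (0.1116 + 0.0380 + 0.0081 + 0.0010 + smaller terms) = 0.318. For a gap of at least 6, P = 0.094.
- K = 17 or 19: P(at least 4) = 0.18. K = 11: 0.15. K = 9: 0.12.
- With an even K only even gaps are possible, and with an odd K only odd ones, so the result moves up and down as K changes. From K = 9 to K = 19 it lies between 12% and 32%. With fewer hard eyes it can be lower (9% at K = 7).
- If instead each eye is hard at random with probability 20%, 30% or 50%, P(at least 4) is 14%, 20% or 24%, and P(at least 6) is 2%, 4% or 6.5%.

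**2. Shift in the arm difference.** Shift = gap × extra loss in hard eyes. For a 4-eye gap:
- 0 points extra: 0
- 5 points: 0.222 × 5 = 1.1 points
- 10 points: 0.222 × 10 = 2.2 points

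For scale, the standard error of the arm difference is SD × √(2/18) = 3.3 to 4.2 points at SDs of 10 to 12.5.

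**3. Error rates, simulated with no device effect.** Hard share 20% to 50%, extra loss 5 or 10 points, within-grade SD 6 to 10.

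| | All trials | Trials with a gap of 20 points or more |
|---|---|---|
| Unadjusted t-test | about 5% | 6% to 14% |
| Linear model with arm and grade | about 5% | 4.5% to 5.2% |

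**4. Precision.** With half the eyes hard, adjustment is worth a factor of 1/(1 - 0.25 × e²/SD²) in eyes, where e is the extra loss.
- e = 0: 1.00
- e = 5: 1.04 (SD 12.5) to 1.07 (SD 10)
- e = 10: 1.19 (SD 12.5) to 1.33 (SD 10)

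The range is therefore 0% to 33% more eyes. The top of it needs the largest assumed effect, the smallest SD and an even mix.

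**5. Cost if grade is not prognostic.** The interval widens through one lost degree of freedom (ratio of t quantiles 1.001 at 36 eyes, 1.002 at 28) and through chance correlation r between arm and grade (mean of 1/√(1 - r²): 1.015 and 1.020). The products are 1.016 and 1.022, or about 2%.

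**The case against.** The strongest reply is that randomisation already accounts for chance imbalance. Averaged over all allocations the unadjusted test holds 5%, and the likely shifts are smaller than one standard error. That stands: the plan's test is valid. What remains is conditional. Once a particular imbalance is drawn, the planned analysis cannot allow for it.

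The second reply is that grade is not shown to matter. That also stands. A reader might infer from the grade I-IV range and from 2.1.2 that grade is an established driver of cell loss in this trial. Section 2.1.2 concerns the whole LOCS III system and surgical planning, and no section ties grade to CEC loss. An effect of zero therefore belongs in the range.

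A reader might also set the 2.2 points against the 5% margin and conclude that imbalance could decide the safety verdict. The documents do not support this. The margin is a sample-size input, set on a proportion, and the safety rule in 10.1.2 does not use it.

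Finally, a reader might conclude that unstratified allocation is itself a flaw. It is a legitimate choice for a 36-eye pilot. Its absence is also read from the silence of 7.3: the IWRS specification was not available, and information on the third party that generates the list is held on file. Stratifying without blocks would not help in any case. In simulation with 18 hard and 18 soft eyes, simple randomisation within each grade stratum left the chance of a gap of 20 points or more at 24%.

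**Conclusion.** The point holds in a limited form. The plan requires a baseline judgement on every eye and then makes no use of it in the primary CEC comparison. A gap of 4 or more hard eyes has a chance of about 12% to 32% (for 9 to 19 hard eyes among 36, arms of 18). Such a gap would move the arm difference by 0 to 2.2 points at an assumed 0 to 10 points of extra loss. Adjustment is worth 0% to 33% more eyes at assumed SDs of 10 to 12.5. The type I error over all randomisations is not in question. Because every effect size here is assumed and the planned test is valid, this is an improvement to consider. It is not a correction that the trial depends on.

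**What to change.** In 10.1.2, replace the unadjusted between-arm test of CEC change with a pre-specified linear model containing arm and nuclear grade (I-II versus III-IV). Classify each eye by the higher of opalescence and colour, since 5.1.1 allows either or both. For the non-normal branch, specify a rank-based or permutation version of the same model. A covariate cannot simply be added to the t-test or the Mann-Whitney test, so both branches need rewording.

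State in 7.5.1.1 and the schedule (1.3) that the LOCS III nuclear grade is recorded in the eCRF before randomisation. Neither now names a separate grading step.

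The cost is one eCRF field, the rewording, 1 degree of freedom, and an interval about 2% wider if grade is not prognostic.

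Stratifying the IWRS list by grade is optional and helps only with small permuted blocks within each stratum. With blocks of 4, the simulated gap never exceeded 11 points. Section 7.1 allows more than one centre, so further strata could become sparse. If the list is stratified, the analysis should still carry grade: in those simulations (within-grade SD 8, 10 points extra loss) the unadjusted test rejected in only 2.3% to 2.9% of trials, against about 5% with adjustment. If the list already exists, the adjustment alone is enough.

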7.4 Outcome variables

7.4.1 Primary outcome variables

- Changes in CEC density.
- IOP.

7.4.2 Secondary outcome variables

- Incidence of adverse events.
- Changes in corneal thickness.
- Cellularity in AC.
- Flare in AC.
- Best corrected visual acuity

7.4.3 Exploratory outcome variable

- Transsurgical evaluation investigator's report.

7.4.4 Definition of variables, methods and scales to be used for measurement

Variable	Guy	Unit (symbol)	Measurement method	Normal value	Evaluation time	Statistical test
Of outcome primary						
Endothelial cell count (cornea)	Continuous quantitative	Cells / mm^2	Microscopy speculate	1500-3500	VE and VF	Student t - test Mann-Whitney U Wilcoxon ranks *
Intraocular Pressure	Continuous quantitative	mmHg	Goldmann tonometry	10-21	VE, V1, V2 and VF	Student t test Mann-Whitney U Wilcoxon ranks *
Of outcome secondary						
Events adverse	Discreet	Number of cases (n)	Counting	0	VE, VP, VC, V1, V2 and VF	Student t test Mann-Whitney U*

Events adverse (Bis)	Nominal categorical	Present / Absent	Observation	Absent	VE, VP, VC, V1, V2 and VF	χ^2 or Fisher's exact test
Changes in corneal thickness	Continuous quantitative	μm	Corneal pachymetry	545 ± 40	VE and VF	McNemar test **
Cellularity of the anterior chamber	Qualitative ordinal	Degrees	Biomicroscopy	0= None	VE, V1, V2 and VF	χ^2 or Fisher's exact test
Flare in the anterior chamber	Qualitative ordinal	Degrees	Biomicroscopy	0= No flare	VE, V1, V2 and VF	McNemar test **
AVMC	Discreet	Fraction (-)	Snellen chart	0.6-2.0	VE, V1, V2 and VF	χ^2 or Fisher's exact test
Of outcome exploratory						
Transsurgical evaluation	Qualitative ordinal	Bad (0) / Very good (5)	Observation	...	VC	χ^2 or Fisher's exact test

BCVA, best-corrected visual acuity; ScrV, scrutiny visit; SurV, surgery visit; SchV, scheduling visit; V1-2, 1st / 2nd safety visits; VF, final visit; χ^2 , Chi-square; *For KS/SW, p < 0.05; **When applied

Table 3. Operational definition of variables

The variables, method, and scales used to measure them are described in detail below. They are listed in order according to **Table 3**.

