3.3 Secondary objectives

- To compare the safety of OVD PRO-149 versus Healon® EndoCoat in cataract phacoemulsification surgery and intraocular lens implantation, with the incidence of AEs.
- To compare the safety of OVD PRO-149 versus Healon® EndoCoat in cataract phacoemulsification surgery and intraocular lens implantation, through changes in central corneal thickness.
- To compare the safety of OVD PRO-149 versus Healon® EndoCoat in cataract phacoemulsification surgery and intraocular lens implantation, with the presence of cellularity in postoperative AC.
- To compare the safety of OVD PRO-149 versus Healon® EndoCoat in cataract phacoemulsification surgery and intraocular lens implantation, with the presence of postoperative AC flare.
- To compare the best-corrected visual acuity obtained after cataract phacoemulsification surgery and intraocular lens implantation between PRO-149 and Healon® EndoCoat.

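### Table 3 lists McNemar's test as the only test for corneal thickness in μm, which contradicts section 10.1.2 and cannot serve the between-arm objective

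*Combined protocol and SAP*

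**What the plan says.** - **Objective.** Section 3.3 compares the two devices "through changes in central corneal thickness".
- **Variable type.** The Table 3 row reads "Changes in corneal thickness Continuous quantitative", with μm as the unit and pachymetry as the method.
- **Test listed.** The same row ends "545 ± 40 VE and VF McNemar test", that is, normal value, screening and final visits, then the test. The entry carries a double-asterisk footnote making it conditional on being applicable. No other test appears in the row.
- **What McNemar is for.** Section 10.1.2 places it under intra-group differences for qualitative variables and describes it as a test "which is applied to 2x2 contingency tables with a dichotomous trait and pairs of matched subjects".
- **What continuous variables get.** For normally distributed data, section 10.1.2 says "Between-group analysis: differences between groups will be analyzed using Student's t-test for independent groups". For non-normal data it names Mann-Whitney U. Within arms it names the paired t-test or Wilcoxon. The synopsis repeats these rules.
- **Flare.** The row begins "Flare in the anterior chamber Qualitative ordinal" and ends "0= No flare VE, V1, V2 and VF McNemar test". Cellularity, also ordinal and assessed at the same visits, ends "0= None VE, V1, V2 and VF χ^2 or Fisher's exact test".

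**The concern.** McNemar's test needs a yes/no trait measured twice on the same subject. Thickness in μm is not such a trait, and the plan gives no cut-point that would make it one. Even with a cut-point, the test would compare each arm with its own baseline and leave the comparison of the arms unanswered.

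Thickness is the only quantitative measure of corneal swelling among the listed outcomes. Section 7.4.4.4 says a pachymetry value is not in itself an adverse event, whatever its change; only clinical decompensation, as judged by the investigator, is. Swelling short of decompensation would therefore show up mainly in the between-arm analysis of thickness. If two sections give that analysis different tests and neither is said to govern, the choice could be made after the data are seen.

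**Working it through.** The plan states no figure on this point, so there is none to reproduce. The check sets the sections side by side and then gives a small illustration.

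**1. Thickness row against the other continuous rows of Table 3**

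| Variable | Type in Table 3 | Test in Table 3 | Between-arm test under 10.1.2 |
|---|---|---|---|
| Endothelial cell count | continuous | t-test, Mann-Whitney, Wilcoxon | t-test or Mann-Whitney |
| Intraocular pressure | continuous | t-test, Mann-Whitney, Wilcoxon | t-test or Mann-Whitney |
| Corneal thickness | continuous | McNemar (when applicable) | t-test or Mann-Whitney |

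Thickness is the only continuous row that departs from 10.1.2.

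**2. Could damaged table cells explain it?** From the second adverse-event row down, the test column alternates: chi-square/Fisher, McNemar, chi-square/Fisher, McNemar, chi-square/Fisher. That is what a shared cell listing chi-square/Fisher with McNemar might look like once split across rows.

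- *Thickness:* on that reading its tests would be chi-square/Fisher plus McNemar. All are categorical, so the entry is wrong either way.
- *Flare:* on that reading it would have chi-square/Fisher between arms and McNemar within arms, as 10.1.2 prescribes for qualitative variables. The flare row may therefore be sound in the original.

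**3. Does the footnote rescue the thickness row?** If McNemar is used only where applicable, it never applies to an undichotomised value in μm. The row is then left with no usable test, and the reader must go to 10.1.2.

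**4. Why within-arm tests cannot replace a between-arm test.** The counts here are hypothetical, with 18 per arm as in section 10.2.1. Assume a dichotomised outcome with every discordant pair in the direction of worsening. The exact two-sided McNemar p-value for d discordant pairs is then 2 × 0.5^d.

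- Worsening in 6/18 and 5/18: the McNemar p-values are 2 × 0.5^6 = 0.031 and 2 × 0.5^5 = 0.063. One arm is nominally significant and the other is not, yet Fisher's exact test between arms gives p = 1.00.
- Worsening in 13/18 and 6/18: the McNemar p-values are 2 × 0.5^13 = 0.0002 and 0.031. Both arms are significant, so the within-arm results look alike, yet Fisher between arms gives p = 0.044.

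The within-arm results can suggest a difference where there is no evidence of one, and can hide one where there is.

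**The case against.** The strongest reply is that 10.1.2 already settles the matter. It assigns between-group tests by variable type: t-test or Mann-Whitney for continuous variables, chi-square or Fisher for nominal and ordinal ones. Section 10.1.1 points to Table 3 for how variables are classified, and Table 3 classifies thickness and flare correctly. On that reading the test column is a clerical slip that the analysis section overrides, and the footnote confirms that McNemar was never meant to apply everywhere.

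Much of this stands. A reader might infer from Table 3 that neither thickness nor flare will be compared between arms at all. The documents do not support that, because 10.1.2 and the synopsis provide a between-arm test for both. A reader might also infer that thickness will be cut at a threshold, with a loss of power. No section plans a cut, so no power loss can be attributed to this plan. For flare, the alternating pattern in the extracted table leaves real doubt about whether there is an error.

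The contradiction on thickness remains. Table 3 is the operational definition of the variables, it names a test that cannot be used, and nothing says that 10.1.2 takes precedence.

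**Conclusion.** The point holds for corneal thickness as an inconsistency between Table 3 and 10.1.2: the listed test fits neither the variable's type nor the objective in 3.3. This does not depend on how the table cells were laid out in the original.

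For flare the finding is only a query. In the extracted text it differs from cellularity, which has the same type and visits, and the original cell should be checked.

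The consequence is modest. Both outcomes are secondary, and the rule in 10.1.2 for declaring the product safe refers only to the primary outcomes. The decision rule, sample size and visit schedule are unaffected. The correction should be made before analysis because it removes a choice of test on a named safety outcome. The p-values in the illustration rest on invented counts and show only the logic.

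**What to change.** 1. **Thickness row of Table 3.** Replace McNemar with a between-arm comparison in μm. The minimum is what 10.1.2 already prescribes: independent-samples t-test or Mann-Whitney on the change from screening to final visit, with paired t-test or Wilcoxon within arms. Preferably, compare final-visit (Day 29) thickness between arms adjusted for screening thickness, and report the difference with a 95% CI. The adjustment goes beyond the plan's present rules but uses a value already collected. With similar variances at the two visits and screening-to-final correlation r, its large-sample variance is about (1 + r)/2 times that of the change-score comparison, so it is no worse. The documents give no r, so no figure is put on the gain.
2. **Precedence.** Add one sentence saying that 10.1.2 governs where it and Table 3 differ.
3. **Flare row.** Check the original cell. Make sure it carries the between-arm test that 10.1.2 requires for ordinal variables, as cellularity does. Keep McNemar, if at all, as a descriptive within-arm result for a dichotomy defined in advance.

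The cost is one corrected cell, one cell to confirm and one sentence. No visit, measurement or sample-size change is needed.

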7.4.4.6 Best Corrected Visual Acuity

Visual acuity (VA) is a test of visual function. Spatial visual acuity is the ability to distinguish separate elements of an object and identify them as a whole. It is quantified as the minimum angle of separation (located at the nodal point of the eye) between two objects that allows them to be perceived as separate objects.

Snellen notation is described as the distance at which the test is performed divided by the distance at which the letter is vertically equivalent to 5 minutes of arc. Thus, at 6 meters a letter 6/6 (20/20) is equivalent to 5 minutes of arc, a letter 6/12 (20/40) is equivalent to 10 minutes, and a letter 6/60 (20/200) is equivalent to 50 minutes. The Snellen fraction can also be expressed as a decimal (i.e., 20/20 = 1 and 20/40 = 0.5).[34]

VA will be assessed at baseline, without refractive correction, using the Snellen chart. This chart will be placed in a location with adequate natural or artificial lighting and at a distance of 3 m from the subject being assessed. Visual acuity will be measured in the study eye, asking the subject to keep both eyes open and using an occluder to cover the contralateral eye. The subject will read aloud the lines indicated by the

evaluator. The line with the smallest letters visible will be recorded by the evaluator as a fraction of the OD VA in the clinical record.

The subject's best refractive correction will then be performed, and the examination will be repeated using the obtained refraction. This result will be reported as best-corrected visual acuity, recorded as a fraction and decimal in both the clinical record and the eCRF.

Management as AE: This value, by itself, will not be considered an AE regardless of the changes; the AE will correspond, in each case, to clinical corneal decompensation when so judged by the PI.

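### Best-corrected visual acuity is stored as a graded decimal but assigned only chi-square or Fisher, with no cut-point or visit named; a between-arm logMAR comparison would use the same data better

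*Combined protocol and SAP*

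**What the plan says.** Section 7.4.2 lists "Best corrected visual acuity" as a secondary outcome, and section 3.3 makes its comparison between arms a secondary objective.

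The acuity row of Table 3 gives the type as 'Discreet', the unit as a fraction, the method as "Snellen chart", the normal value as 0.6 to 2.0, and the times as screening, both safety visits and the final visit. The only test listed is "χ^2 or Fisher's exact test".

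Section 7.4.4.6 has the corrected value "recorded as a fraction and decimal in both the clinical record and the eCRF".

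Section 10.1.2 says that testing for "significant differences in qualitative variables will be performed by creating 2x2 contingency tables", with "Pearson's X^2 test or Fisher's exact test when expected values are less than 5" for the comparison between groups. The significance level is 0.05. The section has rules for continuous and for qualitative variables, and none for discrete ones.

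The other variable typed 'Discreet' in Table 3, the number of adverse events, is given Student's t-test and Mann-Whitney. The synopsis sends quantitative variables in general to those same two tests.

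**The concern.** Acuity is a graded measure with a baseline value, yet its only listed tests treat it as categories. The sole description of those tests is a 2x2 layout, and that needs a cut. No cut is declared. The listed normal value of 0.6 could become one without ever being named as such.

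Two things are at stake. First, splitting a graded measure in two lowers the chance of seeing a real acuity difference in a trial that is already small. In a safety comparison, a missed difference tends to be read as reassurance. Second, when the cut and the visit are both open, the acuity result depends on choices made after the data exist.

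**Working it through.** **Inputs from the plan.** There are 18 eyes per arm (section 10.2.2), of which 14 are required as evaluable (section 10.1.4). Allocation is 1:1 (section 7.3). Alpha is 0.05, taken here as two-sided. Fisher replaces chi-square when an expected count is below 5 (section 10.1.2). The plan has no power, SD or effect size for acuity, so there is no acuity figure to reproduce.

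**Assumptions.** LogMAR is normal with equal SD in both arms, and true differences are 0.8 or 1 SD. None of this is in the documents.

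**Step 1: information kept by a single cut.** The large-sample efficiency of a 2x2 table relative to a t-test is φ(z_q)² / [q(1−q)], where q is the share of eyes on one side of the cut.

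- Median cut: 0.3989² / 0.25 = 0.637, so 36% is lost. Then 18 × 0.637 = 11.5 effective eyes per arm, and 18 / 0.637 = 28.3, so 29 per arm would be needed to match.
- 70/30 cut: 0.576, so 42% is lost.
- 80/20 cut: 0.2800² / 0.16 = 0.490, so 51% is lost.
- 90/10 cut: 0.1755² / 0.09 = 0.342, so 66% is lost.

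The median is the best case, so 36% is a floor for normal data.

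**Step 2: power under the protocol's own rule.** Let p1 and p2 be the shares beyond the cut in each arm. Power is the sum over all i, j from 0 to 18 of Bin(i; 18, p1) × Bin(j; 18, p2), counting tables with p ≤ 0.05. Uncorrected chi-square is used, or Fisher if any expected count is below 5.

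- Central cut, midway between the arm means, 1 SD: p1 = 1 − Φ(0.5) = 0.31 and p2 = 0.69. The expected count is 18 × 0.5 = 9, so Fisher is almost never triggered (about 0.2 to 0.4% of trials).
- 80/20 cut, placed z(0.80) = 0.84 SD above that midpoint, 1 SD: p1 = 1 − Φ(1.34) = 0.09 and p2 = 1 − Φ(0.34) = 0.37. The expected count is 18 × 0.23 = 4.1, so Fisher is used in about 71% of trials.

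| 18 per arm | t-test | Mann-Whitney | 2x2 rule, central cut | 2x2 rule, 80/20 cut |
|---|---|---|---|---|
| 1 SD | 83% | 80% | 70% | 44% |
| 0.8 SD | 65% | 62% | 52% | about 30% (28.8% by enumeration) |

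At 14 per arm and 1 SD, the same calculation gives 72% for the t-test, 49% at the central cut and 28% at the 80/20 cut. At 18 per arm the uncorrected chi-square at a central cut has a true type I error near 6.5%, so its 70% is slightly flattering.

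**Step 3: coarseness of the chart.** Rounding to whole chart lines does little harm. At 0.96 SD and 18 per arm the t-test falls from 80% to between 77% and 79%, with one line taken as 0.67 to 1 SD.

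**Step 4: the other reading.** If a table over chart lines is meant, the mean expected count with k lines in use is 36 / (2k) = 18 / k. At k = 4 this is 4.5, already below 5, and neither test uses the order of the lines.

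**The case against.** The strongest reply is that the plan does not clearly dichotomise acuity. Section 10.1.2 ties 2x2 tables to qualitative variables, Table 3 types acuity as discrete, and the synopsis would send a quantitative variable to the t-test or Mann-Whitney. A reader might infer that a 2x2 split is settled. It is not: the passages conflict, and the 2x2 form is an inference. What remains is that chi-square or Fisher is the only test listed for acuity, and a 2x2 table is the only form described for those tests. The test column also has odd entries nearby (continuous corneal thickness shows only McNemar), so a damaged cell in the PDF reading cannot be excluded.

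A reader might also compare the t-test with Fisher at a central split, which gives about 57% at 1 SD and 38 to 39% at 0.8 SD. That overstates the loss, because the plan reserves Fisher for small expected counts and they are about 9 there. Fisher matters only at uneven cuts.

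Two further inferences go too far. One is that the screening acuity is unused. Section 10.1.2 provides intra-group tests, so it is unused only as a covariate in the comparison between arms. The other is that an open label leaves the cut wholly free. Sections 4.2, 7.3 and 10.1.1 blind the statistical staff, which limits selective choice without replacing a declared cut.

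Finally, the SD-sized effects and normality are assumed. Eyes with disease that limits acuity are excluded, so final acuity may bunch on a few lines. That objection stands against the exact percentages, though not against keeping the graded scale.

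**Conclusion.** The point holds as a conflict in the plan and an inefficient choice of test for a secondary outcome. Under the 2x2 reading at least about a third of the information is lost: 36% at a median cut, and half to two thirds at 80/20 to 90/10 cuts. If 0.6 became the cut and most operated eyes passed it, which is an assumption, the loss would lie at the high end. For a 1-SD difference with 18 per arm, power drops from about 83% to about 70% at a central cut and 44% at an 80/20 cut. These figures rest on normal data and assumed effect sizes. Under the chart-line reading the loss is not quantified here, but the order is ignored and the table is sparse.

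A reader might infer that the trial's safety conclusion is at risk. The documents do not support this: section 10.1.2 bases that conclusion on the primary outcomes alone, the study is a pilot, and no power is claimed for acuity. The change is worth making, but the trial does not stand or fall on it.

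**What to change.** Amend the acuity row of Table 3 and section 10.1.2 as follows.

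- **Scale:** convert the recorded decimal to logMAR as −log10(decimal), so that 1.0 becomes 0, 0.6 becomes 0.222 and 0.5 becomes 0.301. State a convention for off-chart acuity, where the formula has no value to use.
- **Comparison:** name the final visit as the comparison visit, since the plan names none. Compare arms with a linear model adjusted for screening logMAR, and report the mean difference with a 95% CI. The gain from adjustment depends on a correlation that the documents do not give, so none is claimed.
- **Sensitivity analysis:** pre-specify a Mann-Whitney comparison, rather than choosing between methods after a normality test.
- **Descriptive only:** report the proportion reaching an acuity level that is named in advance. State whether the 0.6 in the normal-value column has any role in the analysis.

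The cost is wording in Table 3 and section 10.1.2, plus the off-chart convention. No new measurement, visit or eCRF field is needed.
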